### **2.2.1 Randomization and drug dispensing irregularities**

Not applicable.

## **2.3 ANALYSIS POPULATIONS**

### **2.3.1 Safety populations**

All patients who have signed the ICF will be included in the safety population.

#### **2.3.1.1 Retreated population**

The population is defined as safety patients who have received study drug in TOPAZ study.

#### **2.3.1.2 48 months follow-up population**

The population is defined as all safety patients who have received study drug in CAMMS223, CAMMS323, CAMMS324 or CAMMS03409, that didn't complete 48 months of follow-up at the screening visit in TOPAZ study.

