- During infusion: continuous or hourly monitoring BP/HR; intermittently ambulation, compressive stocking.
- Post infusion: inform/remind patient any abnormal clinical sign/symptoms related to infusion.
- Periodic liver function test.

Please refer to [Section 10.1.6](#) for details.

Study CAMMS03409 is an open-label extension study designed to provide additional safety monitoring for up to 60 months, and as-needed alemtuzumab retreatment to qualifying patients who received alemtuzumab in prior Genzyme-sponsored studies CAMMS223, CAMMS323 and CAMMS324. In addition, patients who received SC IFNB-1a in the earlier studies had the opportunity to receive 2 annual courses of alemtuzumab, and possibly subsequent as-needed alemtuzumab retreatment.

In CAMMS03409, “as needed” retreatment with alemtuzumab could be offered to patients upon documented evidence of resumed MS disease activity, subject to safety-related disqualifications. The additional course(s) of alemtuzumab were administered at 12 mg/day on 3 consecutive days (36 mg total dose) at least 12 months after the prior treatment course. The benefits and risks of >2 treatment courses have not been fully established, but results suggest that the safety profile does not appear to change with additional courses.

The present study LPS13649 will provide long term safety and efficacy data on the patients who completed the extension study CAMMS03409, as well as on additional as-needed alemtuzumab retreatment. In addition, the study will provide information about the safety profile of patients who received other commercial DMTs following alemtuzumab treatment.

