## **7 SELECTION OF PATIENTS**

### **7.1 INCLUSION CRITERIA**

- I 01. Patient has completed at least 48 months of the Extension Study CAMMS03409.
- I 02. Signed written informed consent form (ICF).

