## 9.5.2 Laboratory safety variables

### 9.5.2.1 *Patients exposed to alemtuzumab within 48 months prior to inclusion in this study*

- The following parameters must be obtained at monthly intervals until 48 months after the last infusion of alemtuzumab administered in the study CAMMS03409:
  - CBC with differential (including platelet count).
  - Serum creatinine.
  - Urinalysis (minimally including determination of urine protein and red blood cells) with microscopy.
- TSH must be obtained every 3 months until 48 months after the last infusion of alemtuzumab administered in the study CAMMS03409.
- For women, a Human Papilloma Virus (HPV) screening must be performed as follows:
  - For women within 48 months follow-up at time of study transition from CAMMS03409 to TOPAZ, the date of the last alemtuzumab infusion administered in the study CAMMS03409 must be checked, and then an HPV screening performed approximately 1 year after the last infusion of alemtuzumab, and then every 12 months until 48 months safety FU is completed.

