### 1.4 STUDY PLAN

The whole clinical trial of alemtuzumab consists of three study periods:

CAMMS223/323/324 prior studies (2 years): to compare the efficacy and safety of alemtuzumab to subcutaneous (SC) interferon beta-1a (IFNB-1a, Rebif) in treatment-naïve patients with relapsing-remitting multiple sclerosis (RRMS) who had recent MS disease activity as demonstrated by clinical relapses.

CAMMS03409 extension study (at least 4 years): to examine the long-term efficacy and safety of alemtuzumab in MS patients who received alemtuzumab during prior studies CAMMS223/323/324 and the efficacy and safety of 2 fixed annual alemtuzumab courses in patients who previously received SC IFNB-1a during prior studies.

LPS13649 (TOPAZ) extension study (5 years): to evaluate the long-term safety, efficacy and Quality of life (QoL) of alemtuzumab in patients who have completed at least 48 months of the extension study CAMMS03409.

- ★ Only for patients treated with alemtuzumab: monthly laboratory safety variables collection for 48 months after last infusion
  - For patients who received alemtuzumab in CAMMS03409 study less than 48 months before entering in LPS13649 study, and
  - For patients receiving retreatment with alemtuzumab during the LPS13649 study
- \* After completion of 5 years of the first patient inclusion, the next scheduled visit for any patient will be performed as EOS visit.

Scheduled visits for safety and efficacy assessments will be performed every six months. AEs and concomitant medications will be monitored continuously. Quality of life, pharmaco-economic data and brain imaging will be collected every twelve months (Table 1).

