#### **2.4.5.3 Analyses of laboratory variables**

Laboratory analysis will be conducted for retreated population and 48 months follow-up population. The baselines for each population are defined as below.

- Retreated population baseline: The last non-missing assessment prior to first dose of alemtuzumab in TOPAZ study. The baseline should be taken within 2 weeks prior to the treatment for laboratory assessment except for HPV and pregnancy test. For HPV and pregnancy test, it can be taken in 12 months before the treatment.
- 48 months follow-up population baseline: The last non-missing assessment prior to the last dose of alemtuzumab in previous studies. The baseline should be taken within 2 weeks

prior to the treatment for laboratory assessment except for HPV and pregnancy test. For HPV and pregnancy test, it can be taken in 12 months before the treatment.

The summary statistics (including number, mean, median, Q1, Q3, standard deviation, minimum and maximum) of all laboratory variables (central laboratory values and changes from baseline) will be calculated for each visit or study assessment (baseline, each postbaseline time point, last on-treatment and/or worst on-treatment value and/or other specific assessment) in overall group and by subgroups (IAT vs DAT). This section will be organized by biological function [Section 2.1.4.3](#).

The incidence of PCSAs (list provided in [Appendix A](#)) at any time during the treatment-emergent adverse event period will be summarized by biological function and in overall group and by subgroups (IAT vs DAT) whatever the baseline level and/or according to the following baseline status categories:

- Normal/missing
- Abnormal according to PCSA criterion or criteria

For parameters for which no PCSA criteria are defined, similar table(s) using the normal range will be provided.

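### In the 48-month follow-up laboratory population, IAT patients qualify only through as-needed re-treatment while DAT patients may also qualify on their scheduled courses, so crude at-any-time PCSA percentages are not comparable between the two columns.

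*SAP*

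**What the plan says.** SAP 2.3.1.2 takes patients who had study drug in a core study or in CAMMS03409 and who did not "complete 48 months of follow-up at the screening visit in TOPAZ study". That sentence does not say what the 48 months run from. Other places do: the design notes in SAP 1.4 ("For patients who received alemtuzumab in CAMMS03409 study less than 48 months before entering in LPS13649 study") and Protocol 9.5.2.1, which requires laboratory tests "until 48 months after the last infusion of alemtuzumab administered in the study CAMMS03409". The baseline that SAP 2.4.5.3 sets for this population also precedes the last pre-TOPAZ dose.

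SAP 2.4.5.3 states: "Laboratory analysis will be conducted for retreated population and 48 months follow-up population". By-visit summaries, the incidence of PCSAs at any time and the Kaplan-Meier analysis of liver-test elevation are shown overall and by IAT and DAT. Under the common rules in SAP 2.4.5, the PCSA denominator is the number of patients assessed, and only TOPAZ data plus baseline are used.

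SAP 2.3.3 defines IAT as first alemtuzumab in CAMMS323 or CAMMS324, and DAT as SC IFNB-1a there followed by alemtuzumab in the extension. The extension was to examine, for the latter, "the efficacy and safety of 2 fixed annual alemtuzumab courses in patients who previously received SC IFNB-1a during prior studies" (SAP 1.4). For patients already treated with alemtuzumab, Protocol 4 says "retreatment with alemtuzumab could be offered to patients upon documented evidence of resumed MS disease activity".

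**The concern.** The labels IAT and DAT suggest columns that differ in when alemtuzumab was started. In this population the two groups also have different routes of entry. The IAT route always passes through resumed disease activity and an extra course. The DAT route need not.

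Laboratory change is part of the primary safety endpoint (Protocol 9.1). If the columns differ in re-treatment status and in months of testing left, a difference in the percentage with a platelet, neutrophil, creatinine or liver PCSA could come from those features rather than from immediate or delayed start. No laboratory table is split by re-treatment status, number of courses or time since last infusion, so a reader could not tell these explanations apart.

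**Working it through.** The plan gives no figure to reproduce here; the check is timeline arithmetic.

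**Inputs**
- Core study length 24 months: "CAMMS223/323/324 prior studies (2 years" (SAP 1.4).
- Minimum extension time 48 months: "Patient has completed at least 48 months of the Extension Study CAMMS03409" (Protocol 7.1). The extension runs up to 60 months (Protocol 4).
- Visit 1 within 3 months of extension completion, 6 in the US (Protocol 10.1.1).
- At least 12 months between courses (Protocol 4).
- Assumptions: the extension starts no earlier than the end of the core study, and the two fixed annual DAT courses fall at extension months 0 and 12.

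Let E be months from extension start to TOPAZ D1, including any gap, so E ≥ 48. Let t be months since last infusion at D1. A patient is in the population if t < 48 and then has 48 − t months of required tests left, before any truncation by withdrawal or study end.

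**IAT, core courses only.** With the last infusion at core month c ≤ 24, t = (24 − c) + E. The smallest value is (24 − 24) + 48 = 48, which is already out. With c = 12 (assumed) and E = 48, t = 60. No such patient qualifies, so every IAT member was re-infused after the core study. This does not depend on the number or dates of the core courses.

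**DAT, two scheduled courses only.** t = E − 12, and months left = 48 − (E − 12) = 60 − E.

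| E | t | Months left |
|---|---|---|
| 48 | 36 | 12 |
| 51 | 39 | 9 |
| 54 | 42 | 6 |
| 57 | 45 | 3 |
| 60 | 48 | out |

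For example, 48 extension months plus a 6-month US gap gives E = 54 and 6 months left. If first dosing slipped by 3 months (assumption), months left become 63 − E: 15 at E = 48 and 3 at E = 60.

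**Re-treated in the extension at month r.** t = E − r, and months left = 48 − E + r.
- E = 48: r = 1, 12, 24, 36, 47 leave 1, 12, 24, 36, 47 months.
- E = 60: r = 24, 36, 47, 59 leave 12, 24, 35, 47 months; r = 12 is out.
- A DAT patient's earliest re-treatment is r = 12 + 12 = 24, leaving 24 months at E = 48 and 12 at E = 60.

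**What follows for each table**
- *At-any-time PCSA percentages.* A patient counts once if any test qualifies, over windows from just over 0 to nearly 48 months, with no adjustment. Both composition and number of tests matter.
- *By-visit summaries.* These carry an n at each time point and do not rise with the number of tests. Composition still differs: the baseline precedes course 2 for a scheduled-course DAT patient, but precedes an as-needed course for every IAT patient.
- *Kaplan-Meier liver analysis.* Censoring allows for unequal follow-up. Composition still differs.

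**The case against.** The strongest reply is that the DAT half is conditional. A two-course DAT patient qualifies only with TOPAZ entry less than 48 months after course 2. If DAT patients stayed on schedule to extension month 60, none would qualify and both columns would hold only re-treated patients. The documents give no entry dates. This stands: the IAT restriction is certain on the plan's timeline, the contrast with DAT is possible but not shown, and 12 months is roughly a maximum rather than a typical value.

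Second, SAP 2.4.5 calls the safety analysis essentially descriptive without systematic testing, and SAP 2.4.4 declares the IAT versus DAT comparison for efficacy. A reader might infer that the laboratory tables are planned as a causal comparison of immediate and delayed start; the SAP does not say so. This limits the point to interpretation; no error rate is involved. Descriptive columns can still mislead when their entry rules differ.

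Third, membership is fixed at screening, so a DAT patient re-treated during TOPAZ stays in the population and starts a new 48-month period. The limit of about 12 months therefore applies only to those not re-treated in TOPAZ.

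Fourth, AESIs, including cytopenias, thyroid disorders and ALT increase, already get patient-year rates and tables by number of courses (SAP 2.4.5.1), and courses and person-years are reported by subgroup (SAP 2.4.3.1). That helps with the main signals but does not re-cut the laboratory tables.

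The amount of liver testing is also unclear: Protocol 9.5.2.1 omits liver tests for patients exposed before entry, while Protocol 10.1.6.2 and SAP 2.1.4.3 include them. Those passages must be reconciled before the number of scheduled liver tests can be stated.

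**Conclusion.** The point holds in a conditional form. On the plan's own timeline every IAT member of this population was re-treated before TOPAZ. DAT members may include patients on scheduled courses only, with at most about 12 months of required tests left and none for entry near extension month 60. Crude at-any-time PCSA percentages are then not comparable between the columns; by-visit and Kaplan-Meier results share the composition problem only.

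The size of the distortion cannot be computed, because the documents give neither the share of scheduled-course DAT patients nor entry or re-treatment dates. A reader might infer that the IAT percentage must be the higher one. The documents do not support that: at entry in month 48, an IAT patient re-treated at extension month 1 has 1 month left, against 12 for a scheduled-course DAT patient, while one re-treated at month 36 has 36.

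The conclusion rests on counting the 48 months from the last infusion and on fixed courses at about extension months 0 and 12. An infusion given outside the studies between the extension and Visit 1 is a theoretical exception. This is a cheap improvement to interpretability and leaves the overall safety evaluation intact.

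**What to change.** In SAP 2.4.5.3, for the 48-month follow-up population:

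1. Keep the overall and IAT/DAT columns.
2. Beside each crude PCSA percentage, add incidence per patient-year of laboratory follow-up, or incidence by months since last infusion. State whether person-time stops at a re-treatment in TOPAZ. The rate removes the effect of window length only; the display by months since infusion also shows that scheduled-course DAT patients contribute only late months (about 36 to 48).
3. Add a supplementary split by last pre-TOPAZ infusion: scheduled second course or as-needed re-treatment.
4. Limit any reading of IAT against DAT to as-needed re-treated patients.
5. State in SAP 2.3.1.2 that the 48 months run from the last pre-TOPAZ infusion.

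Infusion dates are already needed to define the population, and the SAP already uses patient-year rates for SAEs and AESIs and splits by number of courses for efficacy. The cost is SAP wording, a few more tables, and small cells in some strata. The supplementary split is itself confounded by disease activity, so it should be presented as descriptive. Replacing the IAT/DAT columns altogether is not needed.

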### **2.3.2 Efficacy populations**

The population on which efficacy analyses will be performed consists of all enrolled patients who have received study drug in CAMMS223, CAMMS323, CAMMS324 or CAMMS03409.

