#### **11.3.2 Efficacy populations**

The population on which efficacy analyses will be performed consists of all enrolled patients who have received study drug in CAMMS223, CAMMS323, CAMMS324 or CAMMS03409.

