### **2.3.3 Subgroup population**

All subgroup populations are subgroup of enrolled patients.

Immediate alemtuzumab treatment (IAT) subgroup: Patients who received alemtuzumab 12 mg/day from CAMMS323 or CAMMS324 study.

Delayed alemtuzumab treatment (DAT) subgroup: Patients who received SC IFNB-1a from CAMMS323 or CAMMS324 and then received alemtuzumab 12 mg/day in CAMMS03409 study.

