#### **2.4.4 Analyses of efficacy endpoints**

The efficacy population will be used for all efficacy analyses.

For MRI endpoints, EDSS, questionnaires endpoints, only data collected in TOPAZ study will be used for analysis in addition of baseline information from previous studies. The long-term baseline is defined as the last available assessment prior to first dose of alemtuzumab or SC IFNB-1a administration in prior studies. It will be applied to long-term efficacy analysis.

For relapse endpoints, data from prior studies (CAMMS323, CAMMS324 and CAMMS03409) should be obtained.

The main long-term analysis for efficacy endpoints is IAT versus DAT comparison. The efficacy of immediate alemtuzumab treatment (Subgroup IAT defined in [Section 2.3.3](#)) and delayed alemtuzumab treatment (Subgroup DAT defined in [Section 2.3.3](#)) groups will be compared for relapse related endpoints, EDSS assessment as well as MRI endpoints.

The analysis in reference of long-term baseline in prior studies by total number of alemtuzumab courses (i.e.  $\leq 3$  vs  $> 3$ ) will be summarized as well.

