#### *2.4.4.1.2 Proportion of Relapse free patients*

The proportion of patients with relapse-free each year from prior studies (CAMMS323/324) until the end of TOPAZ study will be estimated based on Kaplan-Meier methods. The complementary log-log transformation will be used to construct 95% confidence intervals. A Kaplan-Meier graph summarizing the event probability over time will be presented by subgroups (IAT vs DAT) and by alemtuzumab courses. Hazard ratio and corresponding 95% confidence interval will be calculated using Cox proportional hazards (PH) regression with robust variance estimation (6). Covariates for the Cox PH model will include analysis groups and geographic region and prior clinical studies. Inference will be based on the Wald test of the log hazard ratio (estimated regression coefficient from the model). The analysis period starts from prior studies (CAMMS323/324) until the end of TOPAZ study.

The Kaplan-Meier (KM) estimates will be summarized for retreated population separately.

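### Relapse rate and relapse-free estimates for about the first 6 years are conditioned on later entry to TOPAZ: probably too favourable, with an effect of unknown sign on IAT versus DAT

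*SAP*

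**What the plan says.** **Who is analysed.** SAP 2.3.2 says the efficacy population "consists of all enrolled patients who have received study drug in CAMMS223, CAMMS323, CAMMS324 or CAMMS03409". Protocol 11.3.2 has the same definition. SAP 2.3.3 adds, for IAT and DAT, that "All subgroup populations are subgroup of enrolled patients". SAP 2.4.4 allows no exception for relapse: "The efficacy population will be used for all efficacy analyses". The entry criterion in Protocol 7.1 is "Patient has completed at least 48 months of the Extension Study CAMMS03409", and taking part was elective (Protocol 11.1).

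**When the clock starts.** SAP 2.4.4.1.1 runs the ARR model from CAMMS323/324 to the end of TOPAZ. SAP 2.4.4.1.2 says the relapse-free proportion "each year from prior studies (CAMMS323/324) until the end of TOPAZ study will be estimated based on Kaplan-Meier methods", and gives the Cox model the same period. SAP 2.5.1 sets the reference date for long-term analyses at first alemtuzumab or SC IFNB-1a treatment in the prior studies.

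**What it is used for.** SAP 2.4.4 names IAT versus DAT as the main long-term efficacy analysis. DAT membership also requires having received alemtuzumab in CAMMS03409 (SAP 2.3.3).

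**What is absent.** The SAP has no delayed-entry adjustment, no comparison of those who stayed with those who left, no count of patients lost between studies and no stated limitation. Disposition percentages use TOPAZ enrollees as the denominator (SAP 2.2).

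**The concern.** Membership of the analysis set is settled at about month 72 or later, but person-time is counted from month 0. Patients who were treated in CAMMS323/324 and left before TOPAZ are dropped from years in which they were observed. Up to about year 6 no one in the set can be censored for dropout, so the Kaplan-Meier estimate is just the relapse-free proportion among people known to have stayed.

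Protocol 11.4.1 frames the aim as the long-term effect in patients who received alemtuzumab, followed from prior-study baseline. A reader will take year-by-year ARR and relapse-freedom in that sense, and no planned output would show that the early years describe a group selected on its future. The two groups are also selected differently, because DAT patients had to stay through the interferon period and then switch. The comparison in years 0 to 2 is therefore no longer that of the randomized core studies.

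**Working it through.** **Conditioned period.** The inputs are 2 years for the core studies and at least 4 years for the extension (SAP 1.4), with the 48-month entry rule (Protocol 7.1). 24 + 48 = 72 months, or 6 years. This is a minimum, since the extension could run up to 60 months (Protocol 4).

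**No plan figure to reproduce.** The documents give no core-study numbers, retention, reasons for leaving or relapse data on leavers. The rest is illustrative, on assumed inputs.

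**Simple ratio.** Let p be the share of starters who enter TOPAZ and R the relapse rate of leavers divided by that of stayers. Then stayers' ARR / full-cohort ARR = 1 / (p + (1 − p)R).

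| p | R = 0.67 | R = 1 | R = 1.5 | R = 2 |
|---|---|---|---|---|
| 0.9 | 1.03 | 1.00 | 0.95 | 0.91 |
| 0.7 | 1.11 | 1.00 | 0.87 | 0.77 |

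For example, p = 0.7 and R = 1.5 gives 1 / (0.7 + 0.45) = 0.87. The ratio gives leavers full 6-year weight. If they contribute half that time on average (assumed), their share of observed person-time at p = 0.7 is 0.15 / 0.85 = 0.176. Against all observed person-time, the ratio at R = 1.5 is then 1 / (1 + 0.176 × 0.5) = 0.92.

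**Simulation.** One million patients; gamma frailty with mean 1 and variance 1; mean ARR 0.2; exit hazard proportional to frailty to the power g, set so that 70% remain at year 6. As a check, the closed-form 6-year relapse-free proportion is 1 / (1 + 0.2 × 6) = 45.5%.

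| g | ARR, stayers | ARR, all, censored at exit | 6-year relapse-free, full cohort | All, censored at exit | Stayers |
|---|---|---|---|---|---|
| −0.5 | 0.232 | 0.216 | 45.5% | 42.3% | 39.2% |
| 0 | 0.200 | 0.200 | 45.4% | 45.5% | 45.5% |
| 0.5 | 0.166 | 0.184 | 45.4% | 47.6% | 50.7% |
| 1 | 0.140 | 0.168 | 45.4% | 49.0% | 54.3% |

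At g = 1 the stayers-only figure is 54.3 − 45.4 = 8.9 points too high. Keeping everyone and censoring at exit leaves 49.0 − 45.4 = 3.6 points, so censoring removes part of the bias but not all of it.

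**IAT versus DAT.** If both groups are selected alike, the rate ratio is unaffected. With R = 1.5 in both, retention of 90% in IAT and 70% in DAT multiplies the IAT/DAT rate ratio by 0.952 / 0.870 = 1.09. Swapping the retention figures multiplies it by 0.870 / 0.952 = 0.91. The documents cannot tell these cases apart.

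**The case against.** A reader might infer that the early results are necessarily too good, or too good by a definite percentage. The documents do not support that. Relapse was not in itself a reason to leave CAMMS03409, because retreatment could be offered on resumed disease activity (Protocol 4), although safety-related disqualifications applied. TOPAZ has no relapse-based exclusion (Protocol 7.2). Some non-entry may have been administrative: the US entry window was widened from 3 to 6 months so that as many patients as possible could enrol (Protocol Appendix E). Assuming only that leavers relapse more often builds a favourable bias into the calculation.

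A reader might also infer that the IAT versus DAT contrast is biased in a known direction, or might quote a fixed share of follow-up as affected. The first is open, as shown above. The second depends on how long each patient is followed in TOPAZ, which varies because the study ends by calendar time from the first patient's enrolment (Protocol 6.2).

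In mitigation, efficacy is secondary, the study is non-comparative, the protocol plans no formal hypothesis tests (Protocol 11.4), and TOPAZ is openly a follow-up of extension completers. ARR is reported by year, so later years can be read separately.

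All of this limits the claim about direction and size. It does not touch the structure. The overall ARR and the relapse-free curve still carry the conditioned years, the curve cannot be split as yearly ARR can, and SAP 2.4.4.1.2 plans a hazard ratio with Wald inference over the same period.

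**Conclusion.** The concern holds as a matter of structure. ARR and relapse-free estimates for about the first 6 years from core baseline are conditioned on staying to TOPAZ, and nothing in the SAP says so. A favourable bias is probable but unproven. At 70 to 90% retained (assumed), stayers' ARR is 0.77 to 0.95 of the full-cohort ARR if leavers relapse 1.5 to 2 times as often, equal to it if leaving is unrelated to relapse, and 1.03 to 1.11 of it if leavers relapse 0.67 times as often. These are illustrations, not estimates for this trial. The effect on IAT versus DAT has unknown sign. Because efficacy is secondary, this is a worthwhile and inexpensive correction to the SAP rather than a threat to the primary safety objective.

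**What to change.** 1. Report ARR and relapse-free estimates for TOPAZ entrants with the clock starting at D1, as a separate analysis.
2. Add a sensitivity analysis from core baseline in all patients treated in CAMMS323/324, grouped by core-study treatment (alemtuzumab 12 mg or SC IFNB-1a) and censored at last contact. Do not require later alemtuzumab: keeping the DAT definition here would guarantee retention through the core study for DAT alone. Because censoring at exit is only a partial remedy, add censoring weights or a stayer-versus-leaver comparison of relapse history.
3. Label the entrants-only curves from core baseline as conditional on TOPAZ entry, and report the numbers lost at each study transition.

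The cost is extra analysis, retrieval of relapse data for non-entrants from the sponsor's own prior studies, and possibly less favourable figures. SAP 2.4.4 already calls for prior-study relapse data but does not say that it covers non-entrants. The label alone costs a sentence.
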